8.5 Clinical Laboratory Results

Clinical laboratory safety assessments include hematology (including coagulation), serum chemistry, and urinalysis.

Clinical laboratory parameters include those listed in the [Appendix 1 Clinical Laboratory Tests \(Central\)](#).

Baseline is defined as the central lab value closest to and prior to the first dose of test article. If no central lab value is available prior to the first dose of study drug, the local lab value that is closest to and prior to the first dose of study drug will be used as baseline. For by visit analyses, central lab values will be used unless no central lab value was obtained in the visit window. In this case, local lab values will be used for the by visit analyses. All lab values (central and local) are used for determination of the overall worst post-baseline value.

Laboratory data will be summarized by timepoint and for the overall worst post-baseline value using descriptive statistics (based on International System [SI] units) for the actual results and change from baseline for hematology and serum chemistry assessments.

Descriptive statistics (based on SI units) for chemistry, hematology and coagulation values and the change from baseline will be summarized by treatment group at each time point, and for the overall worst value post-baseline (which includes unscheduled visits).

[Appendix 2 Directionality of Worst Laboratory Parameters](#) provides the directionality of the worst values for each laboratory parameter.

Clinically notable laboratory values will be determined based on the modified Division of Microbiology and Infectious Diseases (DMID) criteria in [Appendix 3 Modified Division of Microbiology and Infectious Diseases Adult Toxicity Table](#).

Shift tables will be presented to show the number of subjects with a laboratory value with a grade of 0, 1, 2, 3 or 4 at baseline versus the value at each visit. Number and percentage of subjects with at least a 2-grade increase from baseline (based on DMID criteria) will be summarized by treatment arm. Percentages for each laboratory test will be based on the number of subjects with a baseline and post-baseline evaluation of the specific laboratory test. A listing will be provided for subjects who have at least a 2-grade increase from baseline in a given laboratory test.

The number and percentage (based on the number of subjects with a normal level at baseline) of subjects in each treatment group with an elevated transaminase level ($> 3 \times$ upper limit of normal [ULN], $> 5 \times$ ULN, and $> 10 \times$ ULN), an elevated bilirubin level ($> 1.5 \times$ ULN and $> 2 \times$ ULN) will be presented by study visit. A listing of subjects who meet the laboratory criteria for Hy's law at the same visit will also be provided. The laboratory criteria for Hy's law is defined as 1) ALT or AST $> 3 \times$ ULN, ALP $\leq 2.0 \times$ ULN, and total bilirubin > 1.5 ULN and 2) ALT or AST $> 3 \times$ ULN, ALP $\leq 2.0 \times$ ULN, and total bilirubin $> 2 \times$ ULN.

Tabulated results of urine dipstick tests for leukocyte esterase and nitrates will be summarized by treatment group across visits and will include descriptive statistics for the microscopic evaluations for WBCs.

Subject listings of all laboratory data (local and central laboratory data) collected during the study will be provided, including calculated CrCl (using the Cockcroft-Gault equation). Laboratory values outside normal limits will be identified in the subject data listings with flags for low (L) and high (H) as will laboratory values that meet the clinically notable (CN) thresholds.

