 - 1) Since the driver of efficacy is unknown and the mean renal excretion of a 300 mg oral dose is 14.4%, a regimen that maximizes the tolerated dose of omadacycline may provide additional information on the dose necessary for

clinical and microbiologic success in uUTI and allow comparison to the daily dosed omadacycline treatment groups.

- 6) The proposed dosing of 450mg twice daily for 7 days will provide approximately 2x or greater the amount of omadacycline that is excreted into the urine compared to the daily omadacycline treatment groups.
- 7) Blinded review of the first 145 subjects reveals good tolerability. Nausea has occurred in approximately 10% of all subjects with only a single subject (0.7%) reporting vomiting. There has been only one treatment discontinuation due to adverse events of nausea and/or vomiting reported. Therefore, even if all cases of nausea and vomiting were in a single omadacycline treatment group, nausea and vomiting appears lower than observed in PTK0796-UUTI-15103 study.
- 8) Dose-limiting transaminase increases were seen in Phase 1 studies at 600mg IV which is higher than the exposure at 450mg PO twice daily.
- 9) Increases in heart rate following omadacycline are C_{max} associated. C_{max} concentrations with the 450mg PO dose (1077 ng/mL) at steady state are approximately one-half the C_{max} concentration with the 100mg IV dose (2120 ng/mL) suggesting that heart rate increases above 12-17 bpm observed with 100-200mg IV doses in healthy patients is unlikely following 450mg twice daily dosing.

Therefore based on the pharmacokinetic, clinical, and safety data, the 450mg twice daily dose will increase urinary concentration, may provide additional clinical and microbiologic benefit while maintaining the safety profile observed with daily dosing.

In order to minimize the effect of food on exposure and to potentially minimize the impact of nausea and vomiting during the omadacycline loading dose, omadacycline will be dosed twice on Day 1 with each dose administered approximately 2 hours following a light meal. In addition, all even numbered doses will also be administered approximately 2 hours following a light meal. Given the urinary concentrations observed in PTK0796-UUTI-15103 and the expected impact of a light meal, urinary concentrations should remain above the typical omadacycline MIC₉₀ of 2 µg/mL for *E.coli*, the most common uropathogen in uncomplicated cystitis.

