5.1.3 Visit Windows

For efficacy outcomes, the data collected at the EOT, PTE and FFU visits, regardless of when these occur will be utilized in the analysis of the ITT and micro-ITT populations. The CE and ME populations exclusions due to windowing are outlined in [Sections 4.4](#) and [4.5](#).

For each safety outcome and UTISA data, analyses will utilize assessments occurring during the scheduled visit windows (provided in [Table 4](#)). Thus, if a subject has a visit outside the scheduled visit window, for example, a PTE Visit occurred 20 days after the subject's last day of therapy, the assessment will not be summarized with the PTE Visit but will be considered an unscheduled assessment. If a subject does not have an assessment at a scheduled visit and an unscheduled assessment was taken within the window for the time point (for example, 14 days [\pm 2 days] after the subject's first day of therapy for PTE), these assessments will be summarized in the by time point analyses. If more than one measurement is taken during the visit window, the value taken on the scheduled visit will be utilized or if no scheduled visit was done, the first (earliest) measurement in the visit window will be used. If more than one measurement is taken on the same day, the assessment closest to the start of the dose will be used for on-treatment values and the last measurement on the day will be used for post-treatment values. For worst overall post-baseline analyses, all assessments including those obtained from unscheduled visits will be included.

Table 4 Scheduled Study Visits

Study Visit	Study Day	Notes
Baseline	Day -1 or Day 1	Except where indicated, last measurement prior to the first dose of test article. Screening assessments are to be taken within 24 hours prior to randomization if no test article is taken, the date and time of randomization is used in place of randomization date.
On Treatment (note: analysis visit will be each Study Day)	Day 1- 6	As entered in the eCRF* for these visits
EOT	Day 7	Within 2 days following the last dose of test article
PTE	Day 14	14 ± 2 days after the subject's first dose of test article
Final Follow-up (FU)	Day 30 to 37	30 to 37 days after the start of the first dose of test article

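### The liver-threshold table in SAP 8.5 has no any-time post-baseline row, so it can undercount women who ever crossed a named transaminase or bilirubin limit (minor)

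*SAP*

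**What the plan says.** SAP 8.5 plans, by treatment group, the number and percentage of women with transaminases above 3, 5 and 10 times ULN and with "an elevated bilirubin level ($> 1.5 \times$ ULN and $> 2 \times$ ULN) will be presented by study visit". The percentage is "based on the number of subjects with a normal level at baseline".

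SAP 5.1.3 sets what a by-visit safety summary may use:
- For a PTE sample drawn outside its window, "the assessment will not be summarized with the PTE Visit but will be considered an unscheduled assessment".
- "If more than one measurement is taken during the visit window, the value taken on the scheduled visit will be utilized"; if there was no scheduled visit, the earliest value in the window is taken. The highest is never chosen.
- A substitute is allowed when the scheduled assessment is missing "and an unscheduled assessment was taken within the window for the time point".
- Analyses of the worst overall post-baseline value draw on every assessment, unscheduled ones included.

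SAP 8.5 adds that by-visit analyses take the central result and fall back on a local one only if the window holds no central result. For the worst value the rule is wider: "All lab values (central and local) are used for determination of the overall worst post-baseline value". That worst-value analysis is specified as descriptive statistics of the results and their change from baseline.

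**The concern.** A count of women above 3, 5 or 10 times ULN is normally read as the number who ever reached that level. This table answers a narrower question: how many were above it in the one value chosen for each visit.

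The difference matters here because little chemistry is drawn. Protocol 9.4, 9.5.1 and Appendix 1 schedule post-baseline chemistry at EOT, and at PTE only after a clinically significant EOT abnormality. Any other enzyme result would come from an unscheduled check, and such checks tend to be made because a value is being followed.

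Protocol 7.4 also raises liver enzymes when it justifies the added twice-daily arm: "Dose-limiting transaminase increases were seen in Phase 1 studies at 600mg IV which is higher than the exposure at 450mg PO twice daily". A clear count by arm would let readers see whether that reassurance is borne out.

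**Working it through.** No stated figure needs reproducing. The check sets the table rule beside the window rules, and then asks whether another planned output supplies the missing count.

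**1. Results the table omits.** Take a last dose on Day 7 and read the PTE window as study days.
- EOT window (SAP Table 4): up to 7 + 2 = Day 9.
- PTE window: 14 − 2 = Day 12 to 14 + 2 = Day 16.
- Final Follow-up window: Days 30 to 37.
- In no window: Days 10–11 and 17–29.

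A recheck on one of those days enters no by-visit row. Within a window, suppose the scheduled central ALT lies between 2.5 and 3 times ULN and a local repeat is above 3 times. The table uses the first value and shows no case, whereas the worst-value rule would use the second.

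**2. Women who stop early.** Protocol 9.4 and footnote c of Appendix 1 call for the EOT bloods on the day treatment ends, and the EOT window follows the last dose. Suppose the last dose is on Day 3.
- The EOT window runs to 3 + 2 = Day 5, so a sample drawn on stopping is counted.
- A sample first drawn on Day 7 is 7 − 3 = 4 days after the last dose and is out of window.
- The PTE window still starts on Day 12, so a peak on Days 6–11 is in no window.

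**3. Distinct women.** If k1 women are above a limit at EOT and k2 at PTE, the number ever above it at those visits lies between max(k1, k2) and k1 + k2. One case in each row may be one woman or two.

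**4. The two-grade summary.** SAP 8.5 also plans a count and listing, by arm, of women whose toxicity grade rises by two or more. The Appendix 3 grades, starting from a normal baseline (at most 1 × ULN, grade 0), give:

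| Table threshold | Lowest grade | Rise from grade 0 |
|---|---|---|
| ALT/AST > 3 × ULN | 2 (> 2.5 to 5) | 2 |
| ALT/AST > 5 × ULN | 3 (> 5 to 10) | 3 |
| ALT/AST > 10 × ULN | 4 (> 10) | 4 |
| Bilirubin > 1.5 × ULN | 2 (> 1.5 to 2.5) | 2 |
| Bilirubin > 2 × ULN | 2 (> 1.5 to 2.5) | 2 |

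Every woman who crosses a table threshold from a normal baseline therefore meets the two-grade criterion by size. But the criterion begins at 2.5 × ULN for ALT/AST, so it gives an upper bound for the count above 3 times and does not show how many exceeded 5 or 10. For bilirubin it does not separate 1.5 from 2 times. SAP 8.5 does not say whether unscheduled values feed it. The grade shift tables separate 5 and 10 times ULN, but again only at each visit.

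**5. The plan's own precedent.** For vital signs, SAP 8.6 gives clinically notable counts by time point and also an overall post-baseline incidence. The liver thresholds have no such overall count.

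**The case against.** By-visit presentation is what Protocol 12.6.1 asks for with clinically notable laboratory values, so an overall row is an addition and corrects no departure from the protocol. The relevant results also appear elsewhere: the worst-value statistics include unscheduled visits and report a maximum, all local and central results are listed with flags, and the two-grade count captures these women by size. The protocol mentions transaminases as reassurance, since the increases arose at a higher exposure, and its named adverse events of interest are nausea and vomiting.

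All of this stands, and it makes the point minor. It also rules out three stronger readings that a reader might infer:
- *Unscheduled results are left out altogether.* They are not; one inside a window replaces a missing scheduled result.
- *Women who stop early are dropped.* They are not dropped as such. Their EOT bloods are due on the day they stop, inside a window tied to the last dose. They are affected only if that sample is more than two days late, or if a later peak falls between or after the windows.
- *Cases go uncounted in the report.* The undercount is confined to this table.

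What the objection does not supply is a count by arm of women ever above each named multiple, based on all results.

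**Conclusion.** The point holds as a reporting gap. Followed as written, the table can understate how many women ever crossed a named liver threshold, and no other planned count by arm gives that number or says that it uses unscheduled values.

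The documents do not allow the size to be estimated. The days outside every window are calendar days on which no chemistry is scheduled, so their number does not measure lost results. Nor does a missing EOT sample by itself shrink the percentage base, which is fixed by baseline status.

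The weight of one missed woman can be shown under stated assumptions:
- With equal arms and all baselines normal, 225/5 = 45 women and 1/45 = 2.2%.
- If the added arm shares equally in the subjects remaining after the 145 in the blinded review, (225 − 145)/5 = 16 women and 1/16 = 6.3%.

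Adaptive allocation could change both figures, and neither says that any woman will be missed.

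One matter stays open. Table 4 makes each of Days 1–6 an analysis visit as entered in the eCRF, so it is unclear where an unscheduled chemistry result during treatment would be placed.

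**What to change.** In SAP 8.5:
- Add an *any time post-baseline* row for each transaminase and bilirubin threshold, using each woman's highest post-baseline result from all scheduled, unscheduled, local and central samples. SAP 5.1.3 and 8.5 already define this worst-value data set.
- State the denominator of that row: women with a normal baseline, as the table already requires, who have at least one post-baseline result.
- State that the two-grade-increase summary uses the same values.
- Keep the by-visit rows.

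The cost is two sentences and one extra row per threshold, with no new data and no change to any blood draw. Reported counts may be slightly higher. SAP 3.5 provides for SAP amendments approved before database lock.

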9.4 End of Treatment/Day 7 Visit Procedures

The End of Treatment (EOT)/Day 7 evaluation should be conducted on the day of or within the 2 days following the last dose of test article. If the subject voluntarily withdraws or is discontinued from her dosing regimen, these procedures should be performed on that day:

- Subject assessment of UTI signs and symptoms severity (UTISA questionnaire)
- Concomitant medications
- Physical Examination
- Vital signs: body weight, body temperature, blood pressure, heart rate
- Laboratory tests (blood):

- hematology (includes coagulation)
- chemistry
- serum pregnancy test
- Laboratory tests (urine):
 - Urinalysis via dipstick with optional microscopic exam
 - Urine culture
- AEs
- Investigator’s assessment of clinical response
- Accountability of test article

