9.5 Follow-up Phase

9.5.1 Post-Treatment Evaluation (PTE) Visit

The PTE visit should be conducted on Day 14 (+/- 2 days) after the subject’s first dose of test article. This evaluation should also be conducted for any prematurely withdrawn subject. The following assessments will be performed at the PTE visit:

- Subject assessment of UTI signs and symptoms severity (UTISA questionnaire)
- Physical examination
- Concomitant medications
- Laboratory tests (urine):
 - Urinalysis via dipstick with optional microscopic exam
 - Urine culture
- Vital signs: body temperature, blood pressure, heart rate
- Laboratory tests (blood):
 - hematology (includes coagulation) *
 - chemistry *
 - serum pregnancy test

*Note: hematology & chemistry will be performed only if clinically significant abnormalities were noted at EOT
- AEs
- Investigator’s assessment of clinical response

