^o Subjects should receive their first dose of test article within 4 hours after randomization in the office with a light meal. All other doses can be administered by subject at home. Beginning with Dose 3, all consecutive odd numbered doses of the omadacycline tablets and placebo tablets resembling omadacycline should be taken in a fasted state. Beginning with Dose 4, all even numbered doses should be taken approximately 2 hours after a light meal. The total duration of po test article therapy for all subjects will be 7 days. At the EOT visit, subjects will return any remaining unused po test article and site staff will perform accountability.

^p Dose 2 can be taken a minimum of 8 hours and up to 12 hours after Dose 1. Dose 3 should be taken a minimum of 8 hours after Dose 2.

^q PK blood collection to occur on Day 1 (2 hours after first dose of test article) and Day 5.

^r A PTE will occur on Day 14 (\pm 2 days) after the subject’s first dose of test article.

^s A Final Follow-up will occur 30 to 37 days following the first dose of test article. The Final Follow-up may be performed via phone call or another interactive technology.

^t During the Follow-up call/visit if the subject reports symptoms of potential recurrence, additional procedures will be performed.

^u Hematology and serum chemistry will be repeated if any clinically significant abnormalities are noted at the EOT visit.

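### The Hy's law listing in SAP 8.5 counts only elevations found at the same visit, so non-concurrent transaminase and bilirubin elevations are left out and no other planned output pairs them

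*SAP*

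**What the plan says.** SAP 8.5 defines two sets of criteria. The first is "ALT or AST $> 3 \times$ ULN, ALP $\leq 2.0 \times$ ULN, and total bilirubin > 1.5 ULN"; the second is the same with bilirubin above 2×ULN. The listing covers subjects who meet a set at one visit: "law at the same visit will also be provided".

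The chemistry schedule is sparse. The EOT visit "should be conducted on the day of or within the 2 days following the last dose of test article" (Protocol 9.4). At PTE, on Day 14 ± 2, "hematology & chemistry will be performed only if clinically significant abnormalities were noted at EOT" (Protocol 9.5.1). The schedule footnote in Protocol Appendix 1 agrees: "Hematology and serum chemistry will be repeated if any clinically significant abnormalities are noted at the EOT visit". No chemistry is scheduled at Final Follow-up (Protocol 9.5.2).

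The other laboratory outputs in SAP 8.5 work one test at a time:
- Transaminase and bilirubin threshold counts are given separately, by visit, with subjects normal at baseline as the base.
- Worst post-baseline values are taken per parameter, from all central and local results, including unscheduled ones.
- For grade shifts, "A listing will be provided for subjects who have at least a 2-grade increase from baseline in a given laboratory test".
- For everything else, "Subject listings of all laboratory data (local and central laboratory data) collected during the study will be provided", with flags for low, high and clinically notable values.

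**The concern.** A Hy's law screen asks whether one person had both a transaminase rise and a bilirubin rise without marked ALP elevation. With at most two planned post-baseline samples, the two thresholds need not be crossed on the same draw. A subject can exceed both limits during the study and still be missing from the only output designed to bring them together.

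The rule also leaves a detail open. SAP 5.1.3 reclassifies out-of-window visits as unscheduled, and SAP 8.5 does not say whether an unscheduled draw counts as a visit for this listing.

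What is at stake is whether a subject who needs medical review is identified by the planned output or has to be found by matching rows in other listings.

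**Working it through.** The plan states no figure to reproduce here. The check applies its own rules to assumed values.

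**Inputs from the documents**
- Hy's law rule (SAP 8.5): ALT or AST > 3×ULN, ALP ≤ 2×ULN, and bilirubin > 1.5×ULN (or > 2×ULN), all at one visit.
- ALT/AST grades (SAP Appendix 3): Grade 0 < 1.25; Grade 1 1.25–2.5; Grade 2 > 2.5–5; Grade 3 > 5–10 (×ULN).
- Bilirubin grades (SAP Appendix 3): Grade 0 < 1.1; Grade 1 1.1–1.5; Grade 2 > 1.5–2.5 (×ULN).
- Eligibility (Protocol 6.3, exclusion 12): ALT or AST ≥ 3×ULN and bilirubin > 1.5×ULN are excluded, so Grade 1 baselines are allowed for both tests.

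**Assumed for illustration:** the value pairs below; ALP ≤ 2×ULN throughout; a Grade 0 baseline of ALT 0.8 and bilirubin 0.8; a Grade 1 baseline of ALT 2.0 and bilirubin 1.3 (all ×ULN).

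**Rules compared**
- Same visit: ALT > 3 and bilirubin > 1.5 on one draw.
- Any time: highest post-baseline ALT > 3 and highest post-baseline bilirubin > 1.5.
- 2-grade listing: worst post-baseline grade minus baseline grade ≥ 2, separately per test.

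| Case | EOT ALT / bilirubin | PTE ALT / bilirubin | Same visit | Any time | 2-grade listing from Grade 0 | 2-grade listing from Grade 1 |
|---|---|---|---|---|---|---|
| a | 4.0 / 1.0 | 2.5 / 2.2 | no | yes | both tests | neither |
| b | 6.0 / 1.0 | 4.0 / 2.2 | yes, at PTE | yes | both tests | ALT only |
| c | 3.1 / 1.0 | 2.0 / 1.6 | no | yes | both tests | neither |

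Case a in full: at EOT, ALT 4.0 > 3 but bilirubin 1.0 ≤ 1.5. At PTE, bilirubin 2.2 > 1.5 but ALT 2.5 ≤ 3. Neither draw qualifies alone, yet the peaks of 4.0 and 2.2 pass both limits. From Grade 0 each test rises to Grade 2, an increase of 2, so both are listed. From Grade 1 each rises to Grade 2, an increase of 1, so neither is.

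With the 2×ULN bilirubin criterion, the same-visit rule lists b only, and the any-time rule lists a and b (c peaks at 1.6).

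The Grade 1 subject in case a is above the upper limit of normal on both tests at baseline, so she is also outside the base of the threshold tables. Her values appear as flagged entries in the full laboratory listing, where nothing links the two tests.

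**Spacing of the two draws.** For a subject who completes 7 days, EOT falls on Days 7–9 and PTE on Days 12–16. The gap is 12 − 9 = 3 to 16 − 7 = 9 days. It is longer after early discontinuation, because EOT procedures are then done on that day while PTE stays tied to the first dose.

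**The case against.** The strongest reply is that the information is not lost:
- Every local and central value is listed and flagged.
- ALT above 3×ULN and bilirubin above 1.5×ULN are each at least Grade 2, so a subject who starts at Grade 0 is in the 2-grade listing for both tests.
- A clinically significant laboratory abnormality not already part of another diagnosis is also recorded as an adverse event (Protocol 8.15.4) and followed (Protocol 8.15).
- The safety analyses are descriptive (Protocol 12.6.1), and no decision rule in the published text depends on this listing.

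All of this stands. It limits the point to a missing link between two tests, mainly for subjects with Grade 1 baselines, and to a reader having to match listings by subject number.

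Four stronger readings are tempting but not supported:
- A reader might infer that a transaminase rise at EOT followed by bilirubin at PTE is never listed. Case b shows otherwise: if ALT or AST is still above 3×ULN at PTE, the criteria are met there.
- A reader might infer that the PTE repeat exists to follow delayed bilirubin. Its trigger is any clinically significant EOT abnormality, it covers hematology as well as chemistry, and no hepatic purpose is stated.
- A reader might cite the dose-limiting transaminase increases named in the dose rationale as added urgency. Protocol 7.4 places them at 600 mg IV, which it describes as a higher exposure than 450 mg orally twice daily, and offers this as reassurance.
- A reader might attach a zero-event upper confidence bound per arm. That bound reflects arm size and would be the same under any listing rule, so it does not measure what the same-visit rule misses.

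**Conclusion.** The point holds in a limited form. The same-visit rule omits non-concurrent elevations, and no other output in the published text joins ALT/AST with bilirubin across visits. In the assumed examples it lists one of three subjects who pass both thresholds on study. That ratio shows how the rule behaves and does not estimate frequency: the documents give no basis for how many subjects would show this pattern, and the number is probably very small.

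The conclusion rests on reading the rule literally and on the ALP condition being met. It concerns one safety listing and leaves the primary analysis and the stated adaptation rules untouched. It is a cheap improvement to the SAP.

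**What to change.** In SAP 8.5, keep the same-visit listing and extend it to subjects with:
- ALT or AST > 3×ULN at any post-baseline assessment, and
- total bilirubin > 1.5×ULN (separately, > 2×ULN) at any post-baseline assessment, in either order.

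State that all scheduled, unscheduled, central and local values count, as SAP 8.5 already provides for worst post-baseline values. Add a same-visit yes/no column, and show the ALP values with their dates so that the reviewer can judge them.

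The cost is about one sentence and a small programming change on data already collected. SAP 3.5 allows amendments approved before database lock. The downside is possibly one or two extra subjects for medical review, including any whose two elevations prove unrelated.
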